
The goal of this pilot clinical study is to perform a **randomized placebo-controlled study** to assess the beneficial effect of a **3 month-treatment** with BZA/CE vs. *placebo* on glucose homeostasis and body composition in 30 post-menopausal women. The recruitment will be performed at Tulane Health Sciences Center. The following endpoint will be measured ***at the beginning of the study and after 3 months of treatment***. Patients will have a monthly visit with the clinical coordinator.

a) ***Effect of DUAVEE™ on visceral adiposity. Rationale:*** Our preliminary data show that TSEC treatment prevents visceral fat accumulation in ovariectomized female mice with diet-induced metabolic dysfunction.⁹ It also decreases hepatic and skeletal muscle triglyceride accumulation⁹ in these ovariectomized mice. ***Hypothesis:*** BZA/CE will improve visceral obesity in postmenopausal women. ***Design:*** We will determine the effect of a 3 month- treatment with DUAVEE on body mass index (BMI), waist to hip circumference (WHR)-a clinical index of visceral fat accumulation- and

Version Date: 07/26/17

Version Number: 9.0

Page 2 of 17

directly quantify abdominal fat by DEXA Scan. **We expect** that BZA/CE treatment will improve WHR and decrease abdominal fat in postmenopausal women.

b) ***Effect of BZA/CE on glucose homeostasis. Rationale.*** Our preliminary data shows that TSEC treatment decreases fasting and fed blood glucose levels (as a result of improved insulin sensitivity) in ovariectomized female mice with diet-induced metabolic dysfunction.⁹ **Hypothesis:** DUAVEE™ treatment will decrease glucose and insulin levels in postmenopausal women. **Design:** We will determine the effect of a 3 month- treatment with DUAVEE on fasting and fed glucose and insulin levels. **We expect** that BZA/CE treatment will decrease glucose and insulin levels in postmenopausal women.

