c) ***Clinical modelization of the impact of BZA/CE on glucose homeostasis. Rationale.*** Our preliminary data shows that TSEC treatment improves insulin resistance and glucose tolerance in ovariectomized female mice with diet-induced metabolic dysfunction.⁹ **Hypothesis:** DUAVEE treatment will ameliorate insulin sensitivity and glucose tolerance in postmenopausal women. **Design:** We will determine the effect of a 3 month- treatment with DUAVEE™ on glucose homeostasis following an IV-Glucose Tolerance Test (IVGTT) which will be studied using the minimal model. In the minimal model, computer software is used to calculate insulin sensitivity and secretion from the glucose and insulin dynamics observed during the IVGTT.¹⁰⁻¹² Three major independent parameters can be derived: *The insulin sensitivity index (S)* is the measure of the capability for insulin-stimulated glucose uptake; *the acute insulin response to glucose (AIRg)* which is the total insulin release during the first phase of insulin secretion and *the disposition index (DI)* which is the ability of an individual to control blood glucose taking into consideration insulin secretion in the face of the prevailing degree of insulin resistance.¹³ Therefore, the DI a major therapeutic index when assessing a new drug. The IVGTT coupled to the minimal model is the gold standard and provides the most clinically relevant comprehensive metabolic portrait of an individual.¹⁰ **We expect** that BZA/CE treatment will enhance insulin sensitivity (S) and the disposition index (DI) in postmenopausal women.

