Predicted outcome: We can foresee two possible outcomes. The most likely is that a 3 month-treatment with BZA/CE in postmenopausal women decreases visceral adiposity and markers of systemic inflammation and improves insulin resistance and glucose homeostasis. There are several reasons to anticipate these positive results. *First*, CE is already known to improve glucose and energy homeostasis in postmenopausal women¹ and should continue to have the same activity in a TSEC. *Second*, an importantly SERMs like tamoxifen or raloxifene have never shown any beneficial metabolic effect in rodents and humans.¹ Conversely, BZA exhibits a powerful metabolic effect in female mice and accordingly, we expect that it will translate to women. Finally, TSEC shows a beneficial effect on HFD-induced obesity, independently from estrogen deficiency in mice, suggesting that it may also improve obesity in women. For all these reasons, we are confident that BZA/CE anti-diabetic and anti-obesity effects will translate to postmenopausal women. Acquisition of this information is critical to open novel avenues of therapies for postmenopausal women. The second possible outcome is that although our data generated in pre-clinical models are quite convincing and strongly suggests that BZA/CE will improve metabolic health in women, our hypothesis may not prove correct. This pilot study needs however to be performed because if successful, such preliminary data can lead to new therapeutic avenue for post-menopausal metabolic disturbances.

Statistical Methods: According to our preliminary data obtained in mice,⁹ TSEC treatment increased whole body glucose disposal by 30% and enhanced hepatic insulin sensitivity by 75% compared to vehicle. Although a formal power analysis was not feasible in the pilot study, in light of the high precision that is achieved using the minimal model, we can expect similar improvements to be detectable with 30 patients for whole body insulin sensitivity (Si and DI) in this randomized trial. Our statistician will conduct our data analysis. Briefly, a mixed effects statistical model will be used to investigate the within subject differential response to BZA/CE compared to placebo. Statistical significance will be set at $p < 0.05$. Analysis will be carried out using the software package SAS V 9.3, SAS Institute, Inc. Cary, NC.

2. Subject Population

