We will recruit and screened participants with the aim of randomizing 30 women (10 per group). After referral and clearance (see below), the final assessment of eligibility will be performed during a **screening visit** (blood, medical history and physical examination, barriers to participation, questionnaires). Breast exam and/or mammography will be part of the screening to assess eligibility.

Inclusion:

- Post-menopausal women (<5y since final menstrual period) with age between 50-60y
- Symptomatic (hot flashes, vaginal dryness) or asymptomatic
- BMI 26-45 kg/m² (Overweight, Obesity I and Obesity II)
- fasting glucose <125mg/dl
- Triglycerides < 200 mg/dl
- Normal mammogram within past 12 months
- Physician clearance

Version Date: 07/26/17

Version Number: 9.0

Page 4 of 17

Exclusion:

- Amenorrhea from other causes (Hyperandrogenemia and anovulation)
- Type 2 and Type 1 diabetes
- Medications: diabetes or diabetic drugs, estrogen/progestin therapy, antidepressants and antipsychotics, antiretroviral (HIV), oral steroids, weight loss drugs.
- ≤ 3 month washout of birth control pill (often prescribed for postmenopausal symptoms)
- Hysterectomy (partial or complete)
- Contraindications to estrogen treatment (unusual vaginal bleeding, blot clots, hepatic disease, bleeding disorder, past/present history of breast or uterine cancer, pregnant, breastfeeding)

Screening paradigm: Subjects will be recruited through endocrine and other medicine clinics at Tulane University Hospital & Clinic, Tulane-Lakeside Hospital and through referral from the Department of Medicine at Tulane Hospital & Clinic. Importantly, our recruitment efforts will be done with the Section of Reproductive Endocrinology and Infertility in the Department of Obstetrics and Gynecology at Tulane University Health Science Center. We will also use community advertisements and promotional materials (attached).

3. Procedure

Treatment plan: Subject will participate in a randomized scheme as follows:

- a) PLACEBO for 3 months (N=10 patients)
- b) BZA/CE for 3 months (N=10 patients)

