Patients will have intravenous catheters inserted in a vein in each arm. One will be used for blood samples and the other to administer the IVGTT required medications - glucose and insulin. Baseline blood samples will be taken at -15, -10, and -1 min. before glucose is injected intravenously in the dose of 11.4 g/m² body surface area over 1 min. beginning at time 0. Blood samples will then be taken at timed intervals to check glucose levels via the YSI glucose Analyzer. Insulin will be administered intravenously over 30 seconds in the dose of 0.03 U/kg body weight twenty minutes after the glucose administration. Again, blood samples will be taken at timed intervals until the 3 hour IVGTT is completed. A total of 33 blood samples will be collected for both glucose and insulin according to the chart below.

Time (min)	Glucose and Insulin
-15	X
-5	X
-1	X
0	Glucose IV over 60 seconds – 11.4 g/m ² body surface area
+2	X
+3	X
+4	X
+5	X
+6	X
+8	X
+10	X
+12	X
+14	X
+16	X
+19	X
+20	Insulin iv over 30 seconds - -0.03 U/kg body weight
+22	X
+23	X

Version Date: 07/26/17

Version Number: 9.0

Page **6** of **17**

+24	X
+25	X
+27	X
+30	X
+35	X
+40	X
+50	X
+60	X
+70	X
+80	X
+90	X
+100	X
+120	X
+140	X
+160	X
+180	X

Biomarkers of Inflammation: We will measure serum cytokines (Leptin – Insulin – adiponectin – RBP4 - LCN2 – TNFa - IL6 – PAI-1 – FGF21) through high sensitivity ELISAs. These biomarkers will be collected prior to any testing at Visits 2 and 5 after a 12 hour fast.

Endothelial Function Test: This test will be done at Visits 2 and 5 after a 12 hour fast. It is a non-invasive test that uses Peripheral arterial tonometry (EndoPAT) to assess endothelial function.

Specifics of this Endothelial Function Test can be found in the “Addendum to BIM Study” document that is attached to this protocol.

4. Risks

Risks to Subjects: This Human Subjects Research meets the definition of a Clinical Trial.

Version Date: 07/26/17

Version Number: 9.0

Page 7 of 17

Sources of Materials

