Tulane University Health Sciences Center and the Principal Investigators (the persons chiefly responsible for the record) protect the privacy of research subjects and their PHI collected during a research project. Tulane University Health Sciences Center will not use or disclose existing PHI or PHI created during a research project, unless:

- The subject signs both (a) a HIPAA Authorization for use and disclosure of PHI using an approved Authorization Form or other form containing all the elements of legally effective HIPAA authorization and (b) the informed consent to participate in research form approved by the Institutional Review Board (IRB), or
- The IRB grants a waiver to the requirement of obtaining a signed HIPAA Authorization Form, or
- The IRB-approved protocol uses properly de-identified PHI

Version Date: 07/26/17

Version Number: 9.0

Page **9** of **17**

- The IRB-approved protocol uses the limited data set and the Principal Investigator signs a limited data use agreement with the entity that maintains the designated record set.

5. Benefits

We cannot promise benefits from participating in this study but we expect clear improvements of metabolic health for all the women randomized to pharmacological interventions. The results of the study will provide important information about pharmacological intervention with BZA/CE that may help in controlling weight/fat gain in women during early post menopause. This information can contribute to the development of evidence-based recommendations to help manage weight during menopause.

6. Remuneration

Subjects will receive compensation for their time and travel in the form of a Clincard. They will receive \$25.00 for study visits 1, 3, and 4 and \$50.00 for study visits 2 and 5. The Clincard is a reloadable debit/credit card that will be given to each subject upon completion of their first visit. After each completed study visit thereafter, the card will be uploaded with the amount allowed for that visit. The subject will received compensation for each completed study visit. If they complete all study visits, they will receive up to a total of \$175.00. If a subject is withdrawn from the study by either the investigator or sponsor, or withdraws voluntarily, the subject will be compensated only for the study visits they complete.

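### State the baseline term: with two outcome assessments the planned mixed model most naturally reads as a change-score comparison, which is usually less precise than adjusting for baseline

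*Combined protocol and SAP*

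**What the plan says.** The analysis model is one sentence in the statistical methods paragraph of section 1: "a mixed effects statistical model will be used to investigate the within subject differential response to BZA/CE compared to placebo". That paragraph also gives the 0.05 significance level and the software. Nothing in the supplied text says whether the baseline value is a covariate, a time-0 response with its own mean in each arm, or a time-0 response with a mean common to both arms. No analysis scale is named either.

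Section 1 places the outcome measurements "at the beginning of the study and after 3 months of treatment". Section 3 agrees for the inflammation markers: "These biomarkers will be collected prior to any testing at Visits 2 and 5 after a 12 hour fast". It puts the endothelial test at the same two visits. Section 1 also says "Patients will have a monthly visit with the clinical coordinator", but no efficacy measurement is described for the visits in between. There are five study visits but only two outcome assessments.

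On size, section 2 gives a total of 30 women and also 10 per group, while the treatment plan in section 3 lists two arms of 10. The trial is therefore 20 or 30 women, and both sizes are carried through below.

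**The concern.** A within-subject differential response, modelled over two time points, is most directly an arm-by-time interaction. If each arm has its own baseline mean and all pairs are complete, that interaction is exactly the difference in mean change. A change score subtracts the whole baseline value, which amounts to fixing the slope of follow-up on baseline at 1. When the true slope is lower, this adds baseline noise to the comparison that an estimated slope would remove.

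Two things are at stake. The first is precision: with 20 or 30 women and no formal power analysis, information already collected should not be given up. The second is pre-specification: with many outcomes and the baseline term left open, the same data can yield more than one treatment estimate for each outcome.

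**Working it through.** The plan states no power, human SD or correlation, so there is no figure of its own to reproduce.

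**Inputs.** From the documents: two outcome assessments; n = 10 per arm (listed arms) or n = 15 per arm (30 women in two equal arms). Assumed: correlation ρ between baseline and 3 months of 0.5, 0.7 or 0.9; equal variance σ² at both assessments; two-sided 0.05.

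**Step 1: what the natural reading estimates.** An arm-by-time mixed model was fitted to 120 simulated complete trials. Its interaction equalled the difference in mean change to about 1e-15.

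**Step 2: variances.**
- Change score: (2/n) × 2σ²(1 − ρ), on 2n − 2 df.
- ANCOVA: (2/n) × σ²(1 − ρ²) × (2n − 3)/(2n − 4), on 2n − 3 df. The last factor is the cost of estimating the slope.
- Ratio, ANCOVA to change score: [(1 + ρ)/2] × (2n − 3)/(2n − 4).

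The last factor is 17/16 = 1.0625 at n = 10 and 27/26 = 1.0385 at n = 15.

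| ρ | (1 + ρ)/2 | Ratio, n = 10 | Ratio, n = 15 |
|---|---|---|---|
| 0.5 | 0.75 | 0.80 | 0.78 |
| 0.7 | 0.85 | 0.90 | 0.88 |
| 0.9 | 0.95 | 1.01 | 0.99 |

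A separate simulation (20,000 trials per setting) gave 0.80, 0.91, 1.02 and 0.78, 0.88, 0.99.

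**Step 3: break-even.** Setting the ratio to 1 gives ρ = 2/1.0625 − 1 = 0.882 at n = 10 and 2/1.0385 − 1 = 0.926 at n = 15. Allowing for the lost degree of freedom in the t quantile, confidence intervals break even at 0.867 and 0.920. As ρ approaches 1 the loss is capped at 6.25% and 3.85% of the variance.

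**Step 4: detectable difference** at 80% power, in SD units, change score then ANCOVA:
- n = 10: 1.32 and 1.19 (ρ 0.5); 1.03 and 0.98 (0.7); 0.59 and 0.60 (0.9).
- n = 15: 1.06 and 0.94; 0.82 and 0.77; 0.47 and 0.47.

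**Step 5: skewed outcomes.** Take lognormal data with a proportional treatment effect. On the log scale the effect is a shift, the variances stay equal, and step 2 applies with ρ on that scale. Simulation with a CV of 40% at n = 10 gave about 0.80, 0.90 and 1.01 for a 30% rise, a 15% fall and a 30% fall alike.

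On the raw scale the same data behave differently. A proportional effect changes the treated arm's follow-up SD, and so the fitted slope. At n = 10 the slope is 0.57, 0.80, 1.03 for a 30% rise (ρ 0.5, 0.7, 0.9) and 0.42, 0.59, 0.76 for a 30% fall. The variance ratios follow:
- 30% rise: 0.87, 0.96, 1.01
- 15% fall: 0.70, 0.79, 0.86
- 30% fall: 0.64, 0.71, 0.75

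**Step 6: scale and baseline term interact.** For a 30% fall at ρ 0.7 and n = 10, power is 57% for a raw change score, 71% for raw ANCOVA, 71% for a log-scale change score and 76% for log-scale ANCOVA. Much of the raw-scale gain can thus be had by choosing the scale alone.

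**The case against.** The strongest reply is that the plan is unspecified rather than wrong. The sentence is offered as a summary, and the work is left to the trial's statistician. A mixed model with baseline as covariate, or with a common baseline mean, would also fit it. If one of those is intended, nothing is gained beyond writing it down. This stands, and it limits the point to a request to specify the term. A reader might infer that the plan requires change scores, or that its result would be biased. The documents do not say the first, and randomisation rules out the second.

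It is also true that ρ, the human CV and the human effect size are all assumed; the 30% and 75% in the statistical methods paragraph come from mice. The gain is modest at ρ 0.7 and gone near 0.9.

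A second tempting inference concerns direction. The plan expects that "BZA/CE treatment will enhance insulin sensitivity (S) and the disposition index (DI) in postmenopausal women" and that "BZA/CE treatment will decrease glucose and insulin levels in postmenopausal women". From the raw-scale ratios a reader might conclude that adjustment helps little for SI and DI and much for insulin. That pattern comes from analysing proportional effects on the raw scale. The plan names no scale, and on the log scale the pattern disappears.

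Nor do the documents support saying that very stable outcomes such as BMI or DEXA fat would gain nothing. No correlation is given for them; the scanner SDs and CVs in section 3 are not baseline-to-3-month correlations. A fall analysed on the raw scale at ρ 0.9 still gave ratios of 0.75 to 0.86 in step 5.

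**Conclusion.** The point holds as one of precision and pre-specification, not validity. It should be acted on, with medium confidence because the size rests on assumed inputs. For ρ between 0.5 and 0.7 and equal variances, adjusting for baseline removes about 10 to 20% of the variance at 10 per arm and about 12 to 22% at 15 per arm. Near ρ 0.9 the two methods are about equal.

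These figures rest on complete pairs, a randomised comparison of two equal arms, and either equal variances or log-scale analysis of proportional effects. No gain is claimed for any particular outcome. The unresolved total of 20 or 30 women does not change the conclusion.

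**What to change.** Add to the statistical methods paragraph in section 1:

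> For each outcome the treatment effect at 3 months is estimated by ANCOVA with arm and the baseline value as covariate (both values log-transformed for right-skewed outcomes such as insulin, SI, DI and cytokines), reported with a 95% CI.

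Fix this before outcome data are examined by arm. Section 1 targets an end in September 2015 and this version is dated July 2017. If outcomes have already been examined by arm, the plan should say so, because the choice could no longer be called pre-specified.

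To stay within the plan's model class, a mixed model with a common baseline mean and an unstructured covariance is an equivalent choice. Kenward-Roger degrees of freedom suit the sample size. Women without a Visit 5 value can stay in that model. Its treatment estimate matched ANCOVA on completers to 5 decimals in 8 simulated trials of 10 per arm with 0, 2 or 4 women missing follow-up, so it creates no competing result. One of the two should be named, not both.

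The cost is one sentence, a few lines of code and no new data. The statistical price is one degree of freedom (17 instead of 18, or 27 instead of 28) and the small variance loss in step 3 if ρ is near 1. Log-scale effects would be reported as ratios.

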BZA/CE group: Participants assigned to BZA/CE will receive a daily tablet containing conjugated estrogens 0.45 mg and bazedoxifene 20 mg. BZA/CE (bazedoxifene/conjugated estrogens) tablets, 0.45 mg/20 mg are oval, biconvex, pink tablets, branded with "0.45/20" in black ink on one side. The recommended and only FDA approved dosage is one BZA/CE tablet daily, taken without regard to meals ¹⁴. Tablets should be swallowed whole. If a dose of BZA/CE is missed, participants will be instructed to take it as soon as remembered unless it is almost time for the next scheduled dose. They should not take two doses at the same time. The dose is one tablet per day independent of weight and fat mass. Participants will be provided with information about BZA/CE and its potential side effects and contraindications. Pfizer will provide the medication.

PLACEBO group: In addition to receiving a placebo tablet (provided by Pfizer), participants assigned to the placebo group will be counseled on how to adapt to changes associated with menopause.

DEXA scans: will be performed using a Hologic QDR 4500A whole-body scanner. The scan takes about 5 – 15 minutes and the radiation dose is less than 1 mrem, equal to about 12-h of background radiation. The scans are analyzed with the QDR for Windows V11.1 software. In our hands, the SD is 320 g (CVs of 0.6%) and 300 g (CVs of 1.1%) for FFM and FM, respectively. We will also use the DXA data to estimate muscle mass.

Glucose and insulin: Fasting glucose and insulin will be measured after the 12-h overnight fast. Insulin levels will be collected at each time point during the IVGTT which is described below.

IV-Glucose Tolerance Test (IVGTT): The intravenous glucose tolerance test (IVGTT) interpreted with the minimal model provides individual indexes of insulin sensitivity (S_I) and glucose effectiveness (S_G).

Version Date: 07/26/17

Version Number: 9.0

Page **5** of **17**

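### The protocol randomises 30 women at 10 per group but lists only two arms of 10, a total of 20, and its only sample-size rationale in the available text rests on 30.

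*Combined protocol and SAP*

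**What the plan says.** All the statements below are current text of version 9.0.

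- **Section 1, study goal.** A randomised comparison of BZA/CE with placebo in 30 postmenopausal women.
- **Section 1, Statistical Methods.** On size: "Although a formal power analysis was not feasible in the pilot study", followed by "we can expect similar improvements to be detectable with 30 patients". The planned mixed model addresses the "within subject differential response to BZA/CE compared to placebo".
- **Section 2, Subject Population.** "We will recruit and screened participants with the aim of randomizing 30 women (10 per group").
- **Section 3, Treatment plan.** "Subject will participate in a randomized scheme as follows", and then two entries only: "PLACEBO for 3 months (N=10 patients") and "BZA/CE for 3 months (N=10 patients").
- **Section 3, group descriptions.** There is one paragraph for each of two groups. The first begins "Participants assigned to BZA/CE will receive a daily tablet"; the second covers the placebo tablet and menopause counselling. No other group is described.

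**The concern.** The total and the per-group number cannot both be followed. A team working from the Treatment plan would stop at 20 women. A team working from the study goal, the Statistical Methods paragraph or the total in section 2 would stop at 30.

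The number also carries the only argument for the trial's size. The protocol offers no power calculation, only an expectation stated for 30 patients. If 20 are randomised, that sentence describes a different trial, and nothing in the available text replaces it. The choice also sets the precision of the single between-arm comparison that the analysis plans.

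**Working it through.** **Inputs**

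| Quantity | Value | Source |
|---|---|---|
| Total | 30 | Section 1 study goal; Statistical Methods; section 2 |
| Women per group | 10 | Section 2 |
| Placebo arm | 10 | Section 3, Treatment plan |
| BZA/CE arm | 10 | Section 3, Treatment plan |
| Groups described and compared | 2 | Sections 1 and 3 |
| Significance level | 0.05, sidedness not stated | Statistical Methods |
| SD of Si or DI, target power, dropout rate | none given | – |

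**Step 1: try to reproduce 30.**

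- Listed arms: 2 × 10 = 20. This falls short by 10.
- Three groups: 3 × 10 = 30. This matches, but no third group is described.
- Two arms of 15: 2 × 15 = 30. This matches, but contradicts all three entries of 10.
- Dropout allowance: 20 / (1 − d) = 30 gives d = 1 − 20/30 = 33.3%. No dropout rate is stated, and section 2 gives 30 as the number to randomise, not the number to screen or to complete.
- Unequal allocation: ruled out by two entries of equal size.

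The stated total cannot be obtained from the arms as listed.

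**Step 2: effect on precision.** For two equal arms of n with common SD σ of the analysed outcome (for example, change from baseline), the standard error of the difference is σ√(2/n).

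- n = 10: √(2/10) = 0.447σ
- n = 15: √(2/15) = 0.365σ
- Ratio: √(15/10) = 1.225, so about 22% larger at 10 per arm. The ratio does not depend on σ.

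**Step 3: detectable difference, as an illustration only.** The assumptions are mine: two-sided 0.05, 80% power, a two-sample t-test on change and complete data. The noncentral t distribution gives:

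- 10 per arm (18 df): 1.32 SD
- 15 per arm (28 df): 1.06 SD

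The planned mixed model may give somewhat different precision. Without an SD for Si or DI, these values cannot be converted to a percentage change or set against the 30% and 75% effects in mice that the protocol cites.

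**The case against.** The strongest reply is that this is a pilot with no formal power analysis, so no calculation is overturned. The expectation for 30 patients is extrapolated from mouse data, and going to 20 removes no demonstrated property. That is correct, and it limits what can be claimed: neither 20 nor 30 is shown to be too small. It does not excuse two different totals, since a pilot still needs one number to randomise.

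A second reply is that 30 appears in three places, so the tens could be read as a drafting slip. But 10 also appears three times, two of them in the operative Treatment plan. Counting mentions does not settle the intent.

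A third reply is that the trial may once have had three arms. Three groups of 10 is the only reading under which the sentence in section 2 is consistent with itself, and section 5 (Benefits) mentions interventions in the plural. That is only a hint, because the study goal, the planned analysis and the group descriptions all give two arms. It is still a reason to confirm the number of arms before editing.

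Finally, some pages between the Remuneration section and the end of the main reference list were not available, so nothing is claimed about them. Whatever they say, section 2 and the Treatment plan would still disagree as written.

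**Conclusion.** The inconsistency is real and must be fixed. The protocol states both 30 women and two arms of 10, and nothing in the available text reconciles them. The discrepancy is 10 women in total, or 5 per arm if there are two equal arms. The documents do not show which figure is wrong.

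The arithmetic needs no assumptions. The 22% difference in standard error assumes two equal arms and a common SD. The detectable differences of 1.32 and 1.06 SD rest on the further assumptions in the working and are not needed for the conclusion. Confidence is high.

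**What to change.** First confirm that the trial has two arms. Then state one total and matching arm sizes throughout.

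- **Option 1, 15 per arm.** Keep 30 wherever it appears. Change the per-group figure in section 2 and both arm sizes in the Treatment plan from 10 to 15. This is three number edits. It needs ten more women than the Treatment plan lists (five per arm), but none beyond the stated total of 30.
- **Option 2, 10 per arm.** Keep the three entries of 10. Change 30 to 20 in the section 1 study goal, in Statistical Methods and in section 2. This is also three number edits. It means ten fewer women than the stated total, and Statistical Methods must say whether the expected effects are still thought detectable with 20.

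Under either option, reword the detectability sentence so that it gives the chosen total and the number per arm. A detectable difference in SD units, with its assumptions, could be added but is optional.

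If a third group was in fact intended, the edits above do not apply: that group and its place in the analysis would have to be described.

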d) ***Effect of DUAVEE™ on systemic inflammation. Rationale.*** Our preliminary data show that TSEC treatment improves systemic markers of inflammation and metabolic dysfunction in ovariectomized female mice with diet-induced metabolic dysfunction. Metabolic dysfunction is characterized by recruitment and release of pro-inflammatory cytokines from WAT that cause insulin resistance and a general, low-grade systemic inflammatory state. Our preliminary data show that serum leptin levels and the leptin/adiponectin ratio — a marker of insulin resistance and atherosclerosis — were markedly decreased by TSEC treatment in ovariectomized female mice fed a HFD.⁹ In addition, TSEC treatment decreased serum levels of RBP4, an adipokine that is elevated in insulin resistance and type 2 diabetes.⁹ Further, TSEC treatment reduced serum levels of Lcn2,⁹ an adipokine that is also elevated in adipose tissue and in serum of obese and insulin resistant rodents and humans. Finally, serum levels of TBARS, a marker of oxidative stress and lipid peroxidation, were significantly decreased in OVX mice by TSEC treatment.⁹ Thus, in ovariectomized female mice fed a HFD, TSEC improves adipose dysfunction and systemic inflammation and protect against lipid peroxidation and oxidative stress. **Hypothesis:** BZA/CE treatment will improve systemic markers of inflammation in postmenopausal women. **Design:** We will determine the effect of a 3 month- treatment with DUAVEE on serum cytokines measurement (Leptin - Insulin - adiponectin - RBP4 - LCN2 - TNF α - IL6 - PAI-1 - FGF21). **We expect** that BZA/CE treatment will improve systemic markers of inflammation, lipid peroxidation and oxidative stress in postmenopausal women.

Study Duration: Duration of the recruitment + treatment of patients: 1 year

Target Start and End Dates: October, 2014 – September, 2015.

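### Menopause counselling is stated for the placebo arm and not for the BZA/CE arm, so as written the contrast is the drug effect minus any counselling effect

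*Combined protocol and SAP*

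**What the plan says.** Section 3 (Procedure) describes the two arms in separate paragraphs. The placebo paragraph begins "In addition to receiving a placebo tablet (provided by Pfizer" and goes on to state that "participants assigned to the placebo group will be counseled on how to adapt to changes associated with menopause". The BZA/CE paragraph describes the daily tablet, what to do about a missed dose, and the provision of information on the product, its side effects and its contraindications. It does not mention counselling on menopause.

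Elsewhere the comparator is named only by its short label. The treatment plan lists "PLACEBO for 3 months (N=10 patients" for the control arm. The goal in section 1 is to compare BZA/CE with placebo "on glucose homeostasis and body composition in 30 post-menopausal women". Statistical Methods says that "a mixed effects statistical model will be used to investigate the within subject differential response to BZA/CE compared to placebo".

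One form of contact is described for everyone: "Patients will have a monthly visit with the clinical coordinator". What happens at that visit is not stated.

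**The concern.** A placebo-controlled comparison isolates the drug only if everything else is the same in both arms. Here the text attaches a second intervention to one arm. The endpoints include BMI, waist-to-hip ratio, abdominal fat, glucose, insulin, and the insulin sensitivity and disposition indices from the IVGTT. Changes in diet, activity or adherence could in principle move all of these over 3 months.

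If the counselling prompted such changes, they would occur in the control arm and be subtracted from the drug effect. In a small pilot without a formal power analysis, a real signal could then be missed, or a drug with no effect could look slightly unfavourable.

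**Working it through.** The plan gives no figure for this point, so there is nothing to reproduce. The check is to write out what the planned contrast estimates.

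**Inputs**
- Arm: A = 1 for BZA/CE, A = 0 for placebo (section 3, treatment plan).
- Counselling: C = 1 if given, C = 0 if not. As section 3 is written, C = 1 when A = 0. Nothing is stated when A = 1; following the text literally, C = 0.
- Analysis: change from baseline to 3 months, compared between arms in a mixed model (Statistical Methods). No counselling term is mentioned.
- Assumption: effects add on the scale analysed. Let τ be the change common to both arms (time plus tablet-taking), δ the drug effect and γ the counselling effect.

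**Step 1: the contrast as written.** Expected change = τ + δA + γC.
- BZA/CE: τ + δ
- Placebo: τ + γ
- Difference: (τ + δ) − (τ + γ) = **δ − γ**

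**Step 2: can the model recover δ?** With C = 1 − A, the expected change becomes (τ + γ) + (δ − γ)A. There are two arm means and three unknowns. Adding C as a covariate does not help, because A + C = 1 for every woman and C is therefore collinear with the intercept and arm. Changing the covariance structure or adding baseline covariates does not alter this. The fault lies in the procedure, not in the choice of model.

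**Step 3: the contrast with equal counselling.**
- Both arms counselled: (τ + δ + γ) − (τ + γ) = **δ**
- Neither arm counselled: (τ + δ) − τ = **δ**

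If drug and counselling effects do not add, counselling both arms gives the drug effect among counselled women. That is still a clean drug contrast.

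**Step 4: direction.** The bias is −γ.
- γ in the beneficial direction (up for insulin sensitivity, down for abdominal fat or glucose): the contrast shifts against BZA/CE.
- γ = 0: no bias.
- δ = 0 with beneficial γ: the contrast is −γ, and BZA/CE looks worse than placebo.
- Dropout is a separate route. If counselling alters who returns at 3 months, the sign depends on who is lost, and Step 1 does not determine it.

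**Step 5: size.** The documents give no value for γ and do not describe the counselling from which one could be inferred. The size cannot be derived.

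**The case against.** The strongest reply is that unequal counselling has not been shown. Section 3 never says that only placebo women are counselled, all patients see the coordinator monthly, and the part of the document between Remuneration and the later references was not available to check. This stands as a limit. A reader might infer that BZA/CE women go without counselling, but the text does not say so. It does present counselling as an addition for those assigned to placebo, and nothing available extends it to the other arm. A visit common to both arms does not remove an extra stated for one.

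A second reply is that no text links the counselling to weight or metabolism. That also stands. A reader might look to section 5 (Benefits), which speaks of something that "may help in controlling weight/fat gain in women during early post menopause", and conclude that weight is a counselling topic. The sentence concerns BZA/CE, not the counselling. Section 3 speaks only of adapting to menopausal changes, which could mean symptoms alone.

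A third is that the protocol does not contradict itself, because the short label for the comparator elsewhere is compatible with the fuller description in section 3. This is right. No section says placebo and nothing else, so the point is asymmetry between arms rather than conflict between sections.

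Finally, enrolment may be over. The plan gives "Target Start and End Dates: October, 2014" and an end in September 2015, while this version is dated 07/26/17. The documents do not show whether any women remain to be treated. If none do, only the reporting part of the fix applies.

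**Conclusion.** The point holds in a limited form. Followed as written, the protocol aliases counselling with arm, and the planned comparison estimates δ − γ rather than δ. That rests on the plain reading of section 3 and on additivity. The size of the bias is unknown and may be zero. Its direction is against BZA/CE if counselling improves the endpoints, and undetermined if counselling acts through dropout.

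Three further inferences are tempting, and the documents support none of them:
- **A stated loss of power.** This needs both a counselling effect and a standard deviation of change in women. Neither is given, so any figure would be assumption throughout.
- **Broken blinding.** The available text makes no statement on blinding.
- **Separate analysis of women treated before and after a change of wording, with no pooling.** This is a trade-off and not a requirement. As an assumed example, take 10 women per arm, an SD of log change of 0.30, a 10% counselling effect and an even split. Pooling has bias ½ × ln 1.10 = 0.048 and SE 0.30 × √(2/10) = 0.134, so root mean squared error is √(0.048² + 0.134²) = 0.142. Using only the women after the change has SE 0.30 × √(2/5) = 0.190.

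The uncertain effect and the pilot setting limit the severity. The asymmetry is on the page, though, and resolving it is cheap, so it should be fixed.

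**What to change.** 1. State whether BZA/CE women receive the same menopause counselling. If they do, say so in section 3; nothing else is needed.
2. If they do not, and women remain to be treated, replace the placebo-only sentence with, for example: *All participants, regardless of assignment, receive the same menopause counselling.* Alternatively, remove it from both arms. The content is the sponsor's choice.
3. For women already treated with counselling in the placebo arm only, describe the comparator as placebo plus counselling when the results are reported. If all women have been treated, this is the only step left.

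The cost is one sentence in the protocol and a few minutes of counselling per BZA/CE woman. No extra patients or visits are needed.
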